3.1.2 Protection of Study Participants

A variety of measures have been adopted to ensure the safety of participants in this trial.

- Odanacatib has not been associated with skin or respiratory adverse experiences in clinical or preclinical studies. However, because the adverse experiences of morphea-like skin lesions and upper respiratory tract infections have been reported in a phase IIb study of the non-Merck cathepsin K inhibitor balicatib [5], a regulatory agency has requested that the SPONSOR enroll the current trial in two separate phases. This two-phase approach to study enrollment is designed to avoid unnecessarily exposing large numbers of patients to odanacatib, and to permit study of a limited number of patients with close monitoring by a DMC (safety data review approximately every 4 months) to demonstrate that adverse experiences similar to those seen with balicatib are not associated with odanacatib treatment. In the first phase of enrollment, approximately 1500 patients were randomized in a 1:1 ratio to receive vitamin D₃ (5600 IU once weekly), alone or in combination with odanacatib (50 mg once weekly). Patients also received a sufficient supply of open-label daily calcium supplements, supplied as calcium carbonate, so that their total daily calcium intake (from both dietary and supplemental sources) was approximately 1200 mg.

Product: MK-0822

7

Protocol/Amendment No.: 018-04

Enrollment was interrupted until all 1500 patients in the 'Lead Cohort' had received study drug or placebo for at least 9 months. On December 2008, the 1500 patients completed 9 months of treatment. During this 9-month period, data were reviewed by the DMC approximately every 4 months, corresponding to an incremental increase in study drug exposure of approximately 250 patient-years between DMC reviews. In January 2009, the 9-month safety data were analyzed and reviewed by an independent DMC, which found the data to be reassuring, and recommended that the balance of ~16,300 patients, the 'Main Cohort', resume enrollment into the trial.

- Treatment with intranasal calcitonin not only prior to but actually *during* the study is permitted. This ensures that use of a therapy broadly approved for the treatment of osteoporosis and demonstrated to reduce fracture risk is possible for all study participants irrespective of the study arm to which each patient has been randomized.
- All study participants will be treated with 5600 IU/week of Vitamin D₃. According to a meta-analysis of available clinical trial data, a 26% risk reduction in hip fractures may result from Vitamin D₃ administration at this dose [15]. Supplemental calcium, demonstrated in placebo-controlled trials to confer fracture protection, will be supplied to participants receiving less than 1200 mg daily.
- Annual bone density testing at hip and spine anatomical sites will be conducted in 100% of patients in order to identify women whose bone density is decreasing rapidly (e.g. loss at the lumbar spine or total hip of 7% or greater compared to baseline at any point in the trial). Study participants identified as having excessive bone loss will be discontinued from blinded study therapy and will receive open-label 70 mg once weekly alendronate, or 70 mg once weekly alendronate + 2800 IU cholecalciferol, or 70 mg once weekly alendronate + 5600 IU cholecalciferol from the SPONSOR pending primary physician and Ethics Committee assent.
- The event-driven study design ensures the shortest trial duration that is permissible by regulatory authorities. No study participant will be exposed to possible placebo for longer than is necessary.
- Study participants with >1 prior vertebral fracture are those who have not tolerated or who have refused to take currently available treatments for osteoporosis. Odanacatib may represent the only therapeutic option for such women.
- DMC oversight of this trial ensures that it will be halted "early" in the event that overwhelming evidence of efficacy is acquired. As such, no patient receiving placebo will be deprived of treatment any longer than is required.

3.1.3 Rationale for Study Population

Odanacatib is being developed to reduce the risk of vertebral, non-vertebral and hip fractures in postmenopausal women who are at elevated risk for osteoporotic fracture. Since fracture risk is well-documented to be a function not only of low bone mass, but also of advanced age and a history of prior fracture [16; 17], the trial will be conducted in

Product: MK-0822

8

Protocol/Amendment No.: 018-04

a representative population. The SPONSOR has targeted postmenopausal women who have low bone mass (total hip or femoral neck T-scores ≤ -2.5 for patients without prior vertebral fracture, and total hip or femoral neck T-scores ≤ -1.5 for patients with a prior vertebral fracture), who are over 65 years old. The population will include a significant proportion of patients who have had 1 prior vertebral fracture. This will allow demonstration of efficacy and safety in the population most likely to benefit from this form of treatment.

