2.2 SUBJECT/PATIENT INCLUSION CRITERIA

Note that patients inappropriately randomized into the trial (i.e., those who do not meet entry criteria) may be discontinued from the study at the discretion of the SPONSOR.

- 1) Patient is a woman and is ≥ 65 years of age on the day of Randomization.
- 2) Patient meets one of the following:
 - a) Patient is a candidate for osteoporosis therapy (bisphosphonates, strontium, or PTH), has BMD T-score ≤ -1.5 at either the total hip or femoral neck site, BMD

Product: MK-0822

10

Protocol/Amendment No.: 018-04

T-score ≥ -4.0 at both sites, and has one prior vertebral fracture (defined as anterior, mid or posterior height loss of $>20\%$). – OR-

- b) Patient is a candidate for osteoporosis therapy (bisphosphonates, strontium, or PTH), has BMD T-score ≤ -2.5 at either the total hip or femoral neck site, BMD T-score ≥ -4.0 at both sites, and does not have a prior vertebral fracture (defined as anterior, mid or posterior height loss of $>20\%$). – OR -
- c) Patient is not a suitable candidate for, or has declined osteoporosis therapy (bisphosphonates, strontium, or PTH), has BMD T-score ≤ -1.5 at either the total hip or femoral neck site, and has at least one prior vertebral fracture (defined as anterior, mid or posterior height loss of $>20\%$). – OR-
- d) Patient is not a suitable candidate for, or has declined osteoporosis therapy (bisphosphonates, strontium, or PTH), and has a BMD T-score ≤ -2.5 at either the total hip or femoral neck site, and does not have a prior vertebral fracture (defined as anterior, mid or posterior height loss of $>20\%$).

Note: Eligibility for this criterion is based on absolute BMD in g/cm^2 as follows:
Total hip T-scores of -1.5, -2.5 and -4.0 correspond to 0.759 g/cm^2 , 0.637 g/cm^2 and 0.454 g/cm^2 for Hologic machines; 0.820 g/cm^2 , 0.694 g/cm^2 and 0.506 g/cm^2 for GE Lunar machines, and 0.736 g/cm^2 , 0.614 g/cm^2 and 0.432 g/cm^2 for Norland machines. **Femoral neck** T-scores of -1.5, -2.5 and -4.0 correspond to 0.678 g/cm^2 , 0.558 g/cm^2 and 0.378 g/cm^2 for Hologic machines; 0.830 g/cm^2 , 0.691 g/cm^2 and 0.483 g/cm^2 for GE Lunar machines, and 0.762 g/cm^2 , 0.629 g/cm^2 and 0.430 g/cm^2 for Norland machines.

Note: Patient may not be a suitable candidate for osteoporosis therapy, e.g., due to contraindication, established intolerance, physician's judgment, or patient's unwillingness.

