3.3.1.2 Bone Densitometry

Bone mineral density (BMD) will be measured by dual-energy x-ray absorptiometry (DXA) at the hip (total, femoral neck, trochanter) and lumbar spine for all patients at screening and Randomization, respectively, as well as at yearly intervals until the end of the study. Total body and distal forearm BMD will be measured in a 10% random subset of patients at Randomization and at yearly intervals until the end of the study. End of study BMD will be assessed unless <6 months have elapsed since the time of the last annual BMD measurements. All BMD scans will be centrally evaluated. The BMD QA center will review all baseline scans and confirm patients meet the BMD entry criteria prior to Randomization. The screening Visit 1 hip scan will be used to determine eligibility. Bone densitometry results at the follow-up visits will be blinded to patients and investigators to the extent possible. However, Investigators will be alerted if a patient meets the excessive bone loss criteria (Section 3.4.1.1).

Note: Spine DXA at screening and spine/hip DXA at 6 months will *only* be performed in regions where this is required by regulatory agency via documented request, subsequently approved by the SPONSOR.

All measurements will utilize the same limb and at least 3 vertebrae for all time points (as described in the central vendor DXA manual).

Note: Left hip must be used at screening, unless the left hip is not evaluable. Subsequent hip scans must be performed on the same hip scanned at baseline.

The same machine should be used for a patient throughout the study. Details on DXA acquisition and Quality Assurance will be included in the central vendor DXA manual.

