3.5.5 Statistical Methods

3.5.5.1 Efficacy Analyses

Morphometric Vertebral Fractures

Life-table estimates of the proportion of patients with at least one fracture will be provided for the Month 6 time point and each of the yearly time points, as well as an estimate of the treatment difference and its 95% confidence interval (CI). In the definition of the life-table estimates a patient who does not have a scan at a timepoint (nor later), defined by the time windows in appendix 6.7, will be considered to be censored immediately after the previous time point, since no additional information on the presence/absence of a fracture is available for this patient after the last available scan.

An interval-censored survival approach will be used to evaluate the treatment effect [21; 22]. A generalized linear model for binary data will therefore be used with the complementary log-log transformation of the probability of an event up to the time point, including all available data from the regularly scheduled x-rays. The model will include terms for treatment, stratum (prior/no prior fracture), and geographic region. An estimate of the hazard ratio from the model will be provided along with its 95% confidence interval. The validity of the proportional hazards assumption will be explored (e.g. using the life-table estimates or by investigation of a similar model with treatment-time point interaction added to the model). Consistency of the treatment effect across strata and regions will also be investigated by summary statistics. These analyses and tables will consider only the first fracture per patient. The number (percent) of patients with at least one new morphometric vertebral fracture on the 6-month and yearly x-rays will also be summarized, for each of the treatment groups.

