For non-vertebral, hip and clinical vertebral fractures, since the exact date of the fracture is available in the database, the data will be analyzed using continuous time-to-event methodologies. Kaplan-Meier estimates of the cumulative incidence of first fracture at different time points will be provided, as well as an estimate of the treatment difference and its 95% CI, and the data will be graphically summarized with Kaplan-Meier plots. Treatments will be compared using a Cox Proportional Hazard model with terms for treatment, stratum, and geographic region. Model-based estimates of the hazard ratio, and its 95% confidence interval, will be provided. The validity of the proportional hazards assumption will be explored (e.g. by investigation of similar models with treatment-time or treatment-log(time) interaction added). Consistency of the treatment effect across strata and regions will also be investigated by Kaplan-Meier or hazard ratio estimates within stratum/region.

The proportion of patients with at least one fracture during the first 3 years of the treatment period and the treatment difference, will be estimated using the Kaplan-Meier method.

In addition to these analyses of the first fracture, a summary will also be provided for the number (percent) of patients with 0, 1, 2, more than 2 fractures up to Month 6 and each of the yearly time points.

As a sensitivity analysis, similar analyses will be performed for all adjudicated clinical hip fractures, irrespective if they were osteoporotic (defined as fractures that occur in the absence of trauma or in a low impact trauma setting that would not have resulted in fracture in an individual *without* osteoporosis), traumatic (i.e., secondary to excessive force capable of causing a fracture in an individual *without* osteoporosis), stress or pathological. A similar sensitivity analysis will also be performed for all adjudicated non-vertebral, adjudicated vertebral and all adjudicated fractures.

Stature

The mean (and standard error [SE]) baseline and follow-up height, as well as the mean and 95% CI on the change from baseline will be tabulated for each of the treatment groups and yearly time points.

A graphical presentation of the mean (+/-SE) change from baseline in stature over time will also be provided.

Product: MK-0822

49

Protocol/Amendment No.: 018-04

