3.5.5.4 Sample Size and Power Calculations

Underlying Assumptions

Sample size estimates are based on estimates of fracture incidence rates from the Fosamax Fracture Intervention Trial (FIT) data. It is assumed that the expected relative risk (RR) for morphometric vertebral fractures is 0.5, for non-vertebral fractures 0.8 and for hip fractures 0.65². Sample sizes are based on a 4% alpha level at the final analysis (to account for the interim analyses, see multiplicity adjustment section, the final alpha will be $\geq 4\%$) and 90% power.

To ensure enrollment of a study population with adequate overall fracture risk it was decided to have a flexible sample size depending on the observed ratio of number of patients with a prior vertebral fracture to number of patients without prior vertebral fracture. It is expected that the total sample size needed will be smaller if more patients with a prior vertebral fracture can be included.

For the sample size calculations it is assumed that the recruitment period will be approximately 1 year and the total study duration (including the recruitment period) will be approximately 5 years. Other assumptions used to derive the different scenarios are based on estimates from the FIT data and are detailed in Table 3-12.

² In a recent study of the Novartis compound (ASBMR 28th annual meeting -sep 2006 - S16. Abstract #1054 D. Black et. al.) the relative risk for hip fractures was 0.6.

Product: MK-0822

61

Protocol/Amendment No.: 018-04

Table 3-12

Underlying Assumptions Used for Calculations of Sample Size, Based on FIT Data

Patient Population / Fracture Type	Approximate Placebo Fracture Rate	Relative Risk	Drop-out Rate
Patients with no prior vertebral fracture			
Vertebral fractures	4% at 2 years	0.5	10% with no data at all
Hip fractures	1.4% at 3 years	0.65	20% over 3 years
Non-vertebral fractures	8% at 2 years	0.8	13% over 2 years
Patients with 1 prior vertebral fracture			
Vertebral fractures	8% at 2 years	0.5	10% with no data at all
Hip fractures	3% at 3 years	0.65	20% over 3 years
Non-vertebral fractures	11% at 2 years	0.8	13% over 2 years

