3.5.5.5 Effect of Baseline Factors and Subgroup Analyses

The primary and key secondary endpoints will be summarized by stratum (prior vertebral fracture, no prior vertebral fracture) and the consistency of the treatment effect across strata will be investigated as detailed in Section 3.5.5.1 by summary statistics per stratum.

In addition, for the primary endpoints (morphometric vertebral, non-vertebral and hip fractures), differential treatment effects will be explored across various subgroups, e.g., age, race, baseline BMD T-score tertiles, baseline biochemical marker tertiles, geographic region (e.g., Japan and Far East Region), prior vertebral fracture (0, 1, >1), bisphosphonate intolerance (yes/no), and use of intranasal calcitonin (yes/no). Percent change from baseline in BMD endpoints will also be summarized by bisphosphonate intolerance (yes/no) as well as for patients who are not candidates for or who refuse osteoporosis treatment with bisphosphonates or strontium or PTH versus the other patients. Other subgroups to be investigated are detailed in appendix 6.7. Fracture incidences will be provided for each of the subgroups (by treatment).

Product: MK-0822

66

Protocol/Amendment No.: 018-04

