It was decided to base the futility stopping guideline on the first primary endpoint (morphometric vertebral fractures), while the alpha-, beta-spending functions are based on the number of hip fracture events observed during the trial, for the following reasons: (1) hip fracture has the lowest expected incidence among the 3 types of fracture endpoints, (2) hip fracture reduction is the most difficult to achieve based on both its

Product: MK-0822

70

Protocol/Amendment No.: 018-04

lower incidence, as well as biology. The hip site contains a greater proportion of cortical bone compared to the spine, which has a greater proportion of trabecular bone. Cortical bone has different histology and micro architecture than trabecular bone and also has a slower turnover. (3) Morphometric vertebral fracture risk reduction, by contrast, is expected to be the most easily achieved and the study is highly powered for morphometric vertebral fractures. If this is not achieved, it is highly unlikely that reduction of non-vertebral or hip fracture will be achieved.

Examples of alpha levels for futility are also in Table 3-15.

Table 3-15

Direct Monitoring Using $\alpha(-6,t)$, $\beta(-20,t)$
(Two-sided test at $\alpha=0.050$, α , β -spending function of Hwang, Shih, and DeCani)

Cumulative Information [†]	Stopping for Overwhelming Efficacy			Futility Stopping		
	Alpha at Each Look	Nominal Critical Point		Cumulative Alpha	Alpha at Each Look	Beta Spent
		Lower	Upper			
70%	0.008	-2.645	2.645	0.008	0.990	0.000
85%	0.018	-2.363	2.363	0.020	0.663	0.005
100% [‡]	0.046	-1.994	1.994	0.050	-	0.100

[†] Based on hip fracture events.
[‡] In the final analysis the cut-off level (alpha at the final look) will be calculated for each endpoint separately based on their cumulative amount of data in the interim analyses, and the final alpha will be the minimum of these 3 cut-off levels and will therefore be slightly lower than 0.046.
Depending on the number and timing of the safety updates (before 70% hip fracture events), the actual alpha-levels may be slightly different.

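### The primary fracture models are valid, but adding age and baseline hip BMD, named risk drivers held for every woman, would give a small, nearly free gain

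*Protocol*

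**What the plan says.** Section 3.1.3 gives the reasoning for the study population: "fracture risk is well-documented to be a function not only of low bone mass, but also of advanced age", together with a history of prior fracture.

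The primary models in Section 3.5.5.1 carry one of these three factors, as the stratum:

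- Morphometric vertebral fractures (complementary log-log): "The model will include terms for treatment, stratum (prior/no prior fracture), and geographic region". The GENMOD code in Appendix 6.7 has the same terms plus period.
- Hip, non-vertebral and clinical vertebral fractures: "Treatments will be compared using a Cox Proportional Hazard model with terms for treatment, stratum, and geographic region".

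The other two factors are available at baseline. Age decides entry (Section 2.2: "Patient is a woman and is ≥ 65 years of age on the day of Randomization"). BMD is measured "at the hip (total, femoral neck, trochanter) and lumbar spine for all patients at screening and Randomization, respectively" (Section 3.3.1.2), and hip eligibility is confirmed centrally before randomization. Section 2.2 also gives T-score equivalents for each scanner make.

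For the fracture endpoints, age and BMD appear only among the exploratory subgroups of Section 3.5.5.5, listed as "age, race, baseline BMD T-score tertiles" and others.

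**The concern.** When a plan names strong prognostic factors and holds them for everyone, one expects them in the primary model. Randomization is stratified by fracture history alone (Section 3.2.3.3); the rule that two thirds of women without prior fracture be 70 or older is an enrolment quota, not a stratification factor.

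Stratum is not a stand-in for BMD either. Women with a prior fracture may enter at a T-score of -1.5 or below, while those without need -2.5 or below, so the stratum with the worse fracture history admits higher BMD.

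In a Cox or complementary log-log model, leaving out a prognostic factor pulls the treatment hazard ratio towards 1. Hip fracture sets the size of the trial, so any loss would matter most there.

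**Working it through.** **Inputs (Section 3.5.5.4 unless stated).** "Sample sizes are based on a 4% alpha level at the final analysis"; power 90%; two-sided, as in Table 3-15 ("Two-sided test at" 0.050); 1:1 allocation. Relative risks are 0.65 (hip), 0.8 (non-vertebral) and 0.5 (vertebral). Placebo hip rates are 1.4% and 3% at 3 years, which at the 1:3 mix gives (3 × 1.4 + 3)/4 = 1.8%. Placebo non-vertebral rates are 8% and 11% at 2 years, giving (3 × 8 + 11)/4 = 8.75%. Placebo vertebral rates are 4% and 8% at 2 years, giving 5%.

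**Step 1: reproduce the plan's figures.** Convert each relative risk to a hazard ratio, HR = ln(1 - RR·p)/ln(1 - p), then use Schoenfeld's formula, events = 4(2.054 + 1.282)²/(ln HR)².

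- Hip: HR = ln(0.9883)/ln(0.982) = 0.648, giving 237 events, as stated.
- Non-vertebral: HR = ln(0.93)/ln(0.9125) = 0.793, giving 824 events, as stated.
- Hip power at 237 events and HR 0.65: Φ(½√237 × 0.431 - 2.054) = 89.7% at alpha 0.04. At alpha 0.02 it is 83.9%, against 84% in the protocol.

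**Step 2: effect of omission on hip.** Let s be the SD of the log-hazard due to age and BMD jointly, beyond stratum and region. The documents give no value, so s is an assumption shown as a range. With a normal score X, arm survival is S(t) = E[exp(-H(t)·exp(sX))], calibrated to 1.8% placebo risk at 3 years. The hazard ratio that an unadjusted Cox model estimates over 4 years solves the expected score equation. Power then follows from the Step 1 formula at 237 events, with 0.65 as the conditional hazard ratio.

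| s | HR without age and BMD | Power without | Power with |
|---|---|---|---|
| 0.25 | 0.650 | 89.6% | 89.7% |
| 0.50 | 0.651 | 89.5% | 89.7% |
| 0.75 | 0.652 | 89.2% | 89.7% |
| 1.00 | 0.654 | 88.7% | 89.7% |
| 1.25 | 0.659 | 87.7% | 89.7% |

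**Step 3: simulation check.** In 400 simulated trials of 16,300 women, with and without the covariates, power was 89.0% against 89.3% at s = 0.5 and 89.8% against 90.8% at s = 1.0. With 400 trials, each power has a Monte Carlo standard error of about √(0.9 × 0.1/400) = 1.5 points, so this confirms direction only. The standard error of the log hazard ratio was 0.130 in both models: adjustment does not shrink it.

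**Step 4: the other primary endpoints.** At exactly 824 non-vertebral events and HR 0.80, power would go from 86.0% to 87.5% (s = 0.5) or from 80.3% to 87.5% (s = 1.0). At 114 vertebral events and HR 0.50 (continuous-time approximation) it would go from 94.6% to 95.0%, or from 92.8% to 95.0%. These counts are minimum requirements, however. With 16,300 women, exponential event times, 13% drop-out over 2 years and 3 to 4 years of follow-up, about 1,945 first non-vertebral fractures are expected. Power is then Φ(½√1945 × 0.223 - 2.054) = 99.8% with no added covariate. Section 3.5.5.4 itself states more than 99% for both endpoints.

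**The case against.** The strongest reply is that nothing here is an error. Section 3.1.3 explains whom to enrol and makes no promise about model terms. The models include the stratification factor and region, the test is valid, and age and BMD are explored as subgroups. Stratum and the T-score entry limits restrict what BMD can still explain, so a large s may be unrealistic. The trial is also running under its fourth amendment with regular unblinded monitoring, and changing a pre-specified primary model for at most a point or two of hip power may seem poor value. All of this stands as an argument about size. It does not show that the change is wrong or hard to make.

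A reader might infer three stronger points that the documents do not support:

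- **Useful power gained on all three endpoints.** Two of them already have more than 99%. The several-point gain for non-vertebral fractures needs a stop at exactly 824 events and a large s, whereas the trial must also wait for 237 hip fractures.
- **Exposure to chance imbalance.** With 16,716 women enrolled (Section 3.1.1.1), a standardised covariate differs between arms with a standard error of about 2/√16,716 = 0.015 SD. At s = 1.0 that moves the log hazard ratio by about 0.015, and a 1.96-standard-error imbalance moves it by about 0.03, against a standard error of 0.130.
- **Drop-out that depends on age.** The 20% over 3 years in Table 3-12 is a planning figure from an earlier alendronate trial. Nothing says that it varies with age, and women who stop treatment are to be followed to the end of the trial.

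**Conclusion.** This is a worthwhile minor improvement, not a defect. The fracture models omit two factors that the protocol names as drivers of risk and holds for every woman. The cost is slight attenuation of the hazard ratio: for hip, from 0.650 to between 0.651 and 0.654 at an assumed log-hazard SD of 0.5 to 1.0, or 0.2 to 1 point of power, and about 2 points at 1.25. The result rests on that assumed SD, proportional hazards, a normally distributed score and the rates of Table 3-12. For vertebral and non-vertebral fractures the benefit is an estimate slightly less pulled towards 1.

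**What to change.** In Section 3.5.5.1 and the Appendix 6.7 GENMOD code, add age at randomization and baseline total hip BMD T-score, both continuous, to the complementary log-log and Cox fracture models alongside treatment, stratum and region. Use the same model at every remaining formal interim and at the final analysis. Keep the current model as a sensitivity analysis.

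Make the change by amendment, decided by staff blinded to interim results. Section 3.5 allows amendment of primary analyses, and Section 3.5.1 keeps interim results from the sponsor's blinded team and the unblinded statistician out of amendment discussions.

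No new data are needed. The cost is a documented change to a pre-specified primary model, and a hazard ratio conditional on two more covariates, a very small shift in meaning for hip at these event rates. If the sponsor prefers not to alter the primary model, the adjusted model could instead be pre-specified as the sensitivity analysis.
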